Secondary Endpoint(s)	
1. Severity of bronchoconstriction (as measured by maximum fall in FEV₁ during the aspirin-induced reaction) during the aspirin-induced reaction at Visit 2, compared between patients on placebo vs ifetroban, with the changes also analyzed with provocative aspirin dose as a covariate.
 
2. Increase of urinary, and nasal lavage levels of LTE₄ during aspirin-induced reaction from Visit 2 pre-aspirin levels, compared between patients on placebo vs ifetroban, with the changes also analyzed with provocative aspirin dose as a covariate.
 
3. Change from Visit 1 in baseline FEV₁, Asthma Control Questionnaire (ACQ), and Sino-Nasal Outcome Test (SNOT-22) at Visit 2, compared between patients on placebo vs ifetroban.
 
4. Change in levels of other urinary, and nasal eicosanoids, and levels of plasma/serum and nasal tryptase, from Visit 1 to Visit 2 pre-aspirin challenge and Visit 2 pre-aspirin to during the aspirin-induced reaction at Visit 2, compared between patients on placebo vs ifetroban, with the changes also analyzed with provocative aspirin dose as a covariate.
 
5. Change from Visit 1 in baseline exhaled nitric oxide (FeNO) levels at Visit 2, compared between patients on placebo vs ifetroban.

	6. Change in numbers/percentages of activated platelets and platelet-leukocyte aggregates in the peripheral blood from Visit 1 to Visit 2 baseline (pre-aspirin administration) and during the aspirin-induced reaction at Visit 2 from Visit 2 baseline, compared between patients on placebo vs ifetroban, with the changes also analyzed with provocative aspirin dose as a covariate.
Accrual Objective	50 subjects
Study Duration	36 months
Treatment Description	Ifetroban and aspirin
Inclusion Criteria	
 1. History of AERD, defined as meeting the diagnostic triad with: 
 1. History of physician-diagnosed asthma and 2. History of physician-diagnosed nasal polyposis and 3. History of pathognomonic reactions aspirin or other nonselective COX inhibitors. 2. Stable asthma (post-bronchodilator FEV₁ of ≥70%, no glucocorticoid burst for at least 2 weeks prior to Visit 1, and no hospitalizations or ER visits for asthma for at least the prior 6 months) 3. Age between 18 and 70 years 4. No current smoking (not more than one instance of smoking in the last 3 months) 5. Non-pregnant

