3.3. Secondary Outcomes

The secondary outcomes include the following:

- The severity of bronchoconstriction (measured by maximum percent fall in FEV₁) during the aspirin-induced reaction at Visit 2, compared between patients on placebo vs ifetroban.
- Increase in urinary and nasal levels of cysLTs during aspirin-induced reaction at Visit 2 from Visit 2 pre-aspirin levels, compared between patients on placebo vs ifetroban, as a proof-of-mechanism that TP receptor signaling in AERD drives cysLT overproduction.
- Change in levels of other urinary and nasal eicosanoids, and levels of plasma/serum and nasal tryptase, both from Visit 1 to Visit 2 prior to aspirin administration and also from Visit 2 prior to aspirin administration to during aspirin-induced reactions at Visit 2, compared between patients on placebo vs ifetroban.
- Change in numbers/percentages of activated platelets and platelet-leukocyte aggregates in the peripheral blood between Visit 1 and Visit 2 baseline (pre-aspirin administration) and Visit 2 baseline and during the aspirin-induced reaction at Visit 2, compared between patients on placebo vs ifetroban.

- Change in baseline (pre-aspirin administration) FEV₁, Asthma Control Questionnaire (ACQ), and Sino-Nasal Outcome Test (SNOT-22) at Visit 2 from Visit 1, compared between patients on placebo vs ifetroban.
- Change in Visit 2 baseline (pre-aspirin administration) levels of exhaled nitric oxide (FeNO) from Visit 1, compared between patients on placebo vs ifetroban.
- For each secondary endpoint above, which compares the aspirin-induced changes during the aspirin-induced reaction at Visit 2 for patients on placebo vs ifetroban, we will also analyze these changes with provocative aspirin dose as a covariate. We will treat provocative aspirin dose as level variable: in log scale, if the aspirin doses are 40.5, 81, 162, and 325, we will code the dose variable as dose 1, 2, 3 and 4 assume each increase in dose is linear.

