13.4.4 Analyses of Secondary and Other Endpoint(s)/Outcome(s)

Using a two-sided two-sample t-test for mean difference with unequal variance we will compare each secondary outcome (aspirin-induced fall in FEV_1 , aspirin-induced peak urinary LTE_4 and serum/nasal tryptase) separately on treatment with ifetroban or placebo. Based on our current internal clinical data:

- i. We estimate an average maximum aspirin-induced fall in FEV₁ of 14.6% with a standard deviation of 8.3. With 20 patients per treatment group, we will have 72% power to detect a 50% difference in the fall of FEV₁ at a 0.05 level of significance.
- ii. We estimate an average aspirin-induced peak urinary LTE₄ of 6.0 ng/mg Cr with a standard deviation of 3.9. With 20 patients per treatment group, we will have 74% power to detect a difference of 2.4 ng/mg Cr (or a 40% decrease in the rise in LTE₄) at a 0.05 level of significance.

We will compare each outcome (ifetroban-induced changes in baseline FEV₁, asthma control (ACQ), nasal symptoms (SNOT-22), FeNO and baseline LTE₄) separately after 4 weeks of treatment with ifetroban or placebo using a two-sided two-sample t-test. Based on our current internal clinical baseline data of 25 patients with AERD:

- iii. We estimate an average baseline FEV₁ of 92% predicted and a standard deviation of 9.8, we will have 78% power to detect a difference in FEV₁ of 6%, at a 0.05 level of significance.
- iv. We estimate an average baseline ACQ of 0.64 and a standard deviation of 0.54, we will have 82% power to detect a difference of 0.35 points, at a 0.05 level of significance. A fall in ACQ of 0.5 points is consistent with clinically significant improvement.³³
- v. We estimate an average baseline SNOT-22 score of 38 and a standard deviation of 14, we will have 86% power to detect a difference of 9 points, at a 0.05 level of significance. A fall in SNOT-22 score of 8.9 is consistent with clinically significant improvement.³⁴

We estimate an average baseline urinary LTE₄ of 0.37 ng/mg Cr and a standard deviation of 0.22, we will have 80% power to detect a difference of 0.14 ng/mg Cr (or a decrease in urinary LTE₄ of 30% from baseline, roughly half of the effect of zileuton,^{35,36} at a 0.05 level of significance.

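### The 74% power for peak urinary LTE4 in section 13.4.4 should be about 48%, and four other secondary powers depend on an SD of change that the plan does not give

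*Combined protocol and SAP*

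**What the plan says.** Section 13.4.4 gives six powers for secondary outcomes, all at a 0.05 significance level.

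Items i and ii (maximum fall in FEV1 and peak urinary LTE4 during the aspirin reaction) are introduced with: "Using a two-sided two-sample t-test for mean difference with unequal variance we will compare each secondary outcome". For peak LTE4 the mean is 6.0 ng/mg Cr and the SD 3.9, followed by: "With 20 patients per treatment group, we will have 74% power to detect a difference of 2.4 ng/mg Cr". That difference is described as a 40% decrease. For the fall in FEV1 the stated power is 72%.

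Items iii to v (baseline FEV1, ACQ, SNOT-22) and the closing paragraph on baseline urinary LTE4 concern "ifetroban-induced changes in baseline" values after four weeks, again with a two-sided two-sample t-test. Section 3.3 likewise defines the questionnaire outcomes as the change in "Asthma Control Questionnaire (ACQ), and Sino-Nasal Outcome Test (SNOT-22) at Visit 2 from Visit 1". The source of the SDs is given as: "Based on our current internal clinical baseline data of 25 patients with AERD". The stated powers are 78%, 82%, 86% and, for baseline LTE4, 80%. These four entries give no sample size of their own; section 13.7 sets 20 completers per arm.

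**The concern.** The standardised differences for peak LTE4 and the four change outcomes all lie between 0.61 and 0.65. A two-sample t-test with 20 per arm has roughly even odds of detecting differences of that size, yet the plan states 74 to 86%.

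The LTE4 figure matters most. Section 3.3 presents the aspirin-induced rise in cysteinyl leukotrienes "as a proof-of-mechanism that TP receptor signaling in AERD drives cysLT overproduction". A reader who trusts 74% will take a non-significant LTE4 result as fair evidence against the mechanism, when the trial had about an even chance of missing a 40% reduction. For SNOT-22, the 9 points used for power is practically the 8.9 points that the plan cites as clinically significant, so the stated 86% reads as assurance about a patient-relevant effect.

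**Working it through.** **Method.** With n per arm, difference D and arm SDs s1 and s2, the noncentrality is D / √(s1²/n + s2²/n). Power is the probability that a noncentral t with Welch degrees of freedom exceeds the two-sided 5% critical value in absolute size.

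**Check on the plan's primary figure (13.4.2).** D = 180 − 60 = 120, SDs 42 and 170, n = 20: noncentrality 3.06, df 21.3, power 83.2%. The plan says 83%, so the method matches the plan's.

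**Printed inputs, n = 20 per arm, equal SDs, df 38**

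| Outcome | D | SD | D/SD | Stated | Recomputed | At 25 per arm |
|---|---|---|---|---|---|---|
| Peak LTE4 | 2.4 | 3.9 | 0.615 | 74% | 47.5% | 56.8% |
| Baseline FEV1 | 6 | 9.8 | 0.612 | 78% | 47.1% | 56.4% |
| ACQ | 0.35 | 0.54 | 0.648 | 82% | 51.5% | 61.2% |
| SNOT-22 | 9 | 14 | 0.643 | 86% | 50.9% | 60.5% |
| Baseline LTE4 | 0.14 | 0.22 | 0.636 | 80% | 50.1% | 59.7% |

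The last column counts all 50 recruits with no dropout.

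**Can peak LTE4 reach 74% some other way?**

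- *Smaller SD on ifetroban, placebo SD 3.9.* SD 2.34 (3.9 × 0.6, shrinking with the mean; assumed): 62.8%. SD 1.0: 72.1%. SD 0: 74.2%. Reaching 74% needs an SD of about 0.34, beside an active mean of 6.0 − 2.4 = 3.6.
- *Analysing the increase.* The synopsis defines the endpoint as the rise "during aspirin-induced reaction from Visit 2 pre-aspirin levels". If the pre-aspirin SD equals the plan's baseline figure ("0.37 ng/mg Cr and a standard deviation of 0.22"), the SD of the increase lies between 3.9 − 0.22 = 3.68 and 3.9 + 0.22 = 4.12 whatever the correlation. Power is then 52.0% to 43.5%.
- *A different test.* A paired or one-sample t-test with n = 20 and SD 3.9 gives 74.2%. That matches the stated figure but is not the planned test.

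**Precision.** The expected 95% CI half-width for peak LTE4 is about t(0.975, 38) × 3.9 × √(2/20) = 2.50 ng/mg Cr, wider than the target of 2.4. The difference detectable with 80% power is about 3.5.

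**The four change outcomes.** The SD of change is SD × √(2(1 − r)), where r is the Visit 1 to Visit 2 correlation; it equals the baseline SD only at r = 0.5. The plan gives no r, so the values below are assumed.

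| Outcome | r = 0.3 | 0.5 | 0.7 | 0.8 | Stated | SD of change needed | r needed |
|---|---|---|---|---|---|---|---|
| FEV1 | 36% | 47% | 68% | 85% | 78% | 6.8 | 0.76 |
| ACQ | 39% | 52% | 73% | 89% | 82% | 0.38 | 0.76 |
| SNOT-22 | 39% | 51% | 73% | 88% | 86% | 9.1 | 0.79 |
| Baseline LTE4 | 38% | 50% | 72% | 87% | 80% | 0.15 | 0.76 |

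**Baseline LTE4 percentage.** 0.14 / 0.37 = 38%, whereas the plan says 30%. A 30% fall is 0.3 × 0.37 = 0.11, with power 26%, 34%, 52% and 69% at r = 0.3, 0.5, 0.7 and 0.8.

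**Fall in FEV1 (item i).** D = 0.5 × 14.6 = 7.3; SD 8.3 in both arms gives 77%, against the stated 72%. An ifetroban-arm SD of about 9.4 would give 72%. This mismatch is on the cautious side.

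**The case against.** The strongest reply is that one arithmetic error is being grouped with four missing inputs. For the change outcomes, the 47 to 52% rests on r = 0.5, which is no more stated in the plan than 0.76 is. Patients must have stable asthma, maintenance therapy is largely fixed and the interval is four weeks, so a high correlation is quite possible. All four stated powers fall inside the range for r from 0.3 to 0.8. This stands: those powers are unsupported, not disproved.

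A second point is that the cause may be a wrong n. Two-sample tests with 40 per group and the printed SDs give 77% for FEV1, 82% for ACQ and 80% for baseline LTE4, close to the stated values, but 81% for SNOT-22 against 86%. Forty is the trial's total. Section 13.1 also calls the design a crossover, while the synopsis calls it parallel. Either could explain some figures, but the documents do not show which, and neither would justify them for 20 per arm.

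Third, how much a null LTE4 result excludes depends on the truth. In simulation with SD 3.9 and 20 per arm, about 47% of non-significant results exclude a 2.4 reduction if the true effect is zero, and about 18% if it is 1.2. So such a result leaves 2.4 open more often than not, though only narrowly when there is no effect.

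Finally, these are secondary outcomes, and the sample size does not depend on them. That is true and limits the weight of the point. None of these replies defends the 74%.

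**Conclusion.** The concern holds. Peak LTE4 power is misstated: about 48% with equal SDs, 63% if the ifetroban SD falls with the mean (assumed), and never above 74.2%. Analysed as an increase it is 43 to 52%, taking the baseline SD as the pre-aspirin SD. The powers for baseline FEV1, ACQ, SNOT-22 and baseline LTE4 cannot be checked from the plan. They hold only if r is about 0.76 to 0.79; over r = 0.3 to 0.8 the SNOT-22 power, for example, runs from 39% to 88%. The 30% and the 0.14 ng/mg Cr contradict each other. Item i also fails to reproduce with equal SDs, but is understated. The primary power of 83% and the sample size are unaffected. This should be fixed, but it does not threaten the trial's main comparison.

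**What to change.** Revise section 13.4.4:

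1. Peak LTE4: replace 74% with 48% (equal SDs), or print the SD assumed in each arm with the resulting power. It would help to add that about 3.5 ng/mg Cr is detectable with 80% power at the stated SD.
2. Baseline FEV1, ACQ, SNOT-22 and baseline LTE4: recompute power from an SD of change in the internal data and print that SD. If none exists, withdraw the single figures and give the range over r = 0.3 to 0.8, labelled as assumed.
3. Reconcile 0.14 ng/mg Cr with 30%. The documents do not show which was intended.
4. Fall in FEV1: state the SD assumed in each arm, since the test allows unequal variances and only one SD is printed.
5. State 20 per arm wherever a power is given.

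Separately, bring the crossover description in section 13.1 into line with the parallel design.

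The cost is wording only; enrolment, tests and procedures do not change. The stated LTE4 power becomes clearly less favourable, and the four change outcomes lose their single power figures unless an SD of change is available.

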7.1.2. Other permitted concomitant medications

- **Inhaled, oral or nasal corticosteroids:** Participants may enter the trial on such medications based on the underlying condition. No modifications will be made with the exception of a temporary increase in the dose of oral corticosteroids if worsening asthma requires such an intervention. For those patients who require daily oral steroids for their standard maintenance regimen, they must be on no more than a daily dose of 10mg prednisone or equivalent for their standard daily therapy to be considered for inclusion.
- **Inhaled long acting beta-adrenergic agonists and inhaled ipratropium:** participants may enter the trial on such medications based on the underlying condition. No modifications will be made in the course of the trial.
- **Inhaled short acting beta-adrenergic agonists (PRN use):** participants may enter the trial on such medications based on the underlying condition. No modifications will be made in the course of the trial.

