8.3. Study Visits

Visit 1 After the 2-week Run-In period on montelukast, subjects will come into the ARC for their baseline visit (Visit 1). The following procedures, assessments, and laboratory measures will be conducted:

1. Interval history, physical exam, ACQ, SNOT-22, TNSS and spirometry will be recorded, along with FeNO.
2. Blood will be drawn for CBC/differential, and the cellular profiling and activation assays.
3. A urine sample will be collected for pregnancy and eicosanoid metabolites. Nasal lavage for cytokine and eicosanoid measurements and a nasal epithelial scraping sample for RNA extraction will be taken.
4. Subjects will be randomized to receive ifetroban (200 mg dose per day), or placebo for 4 weeks.

Subjects will take ifetroban or placebo daily for 4 weeks and will continue taking daily montelukast. There will be a telephone encounter (**Phone Call 2**) 1 week into this Treatment Period to ensure safety and confirm that chronic asthma symptoms have not worsened (as assessed by an ACQ-6 score).

Pharmacokinetic studies of ifebtroban have demonstrated that ifetroban absorption is lower, and maximum plasma concentration is lower, if the drug is taken following a meal. To ensure that absorption of the oral ifetroban is consistent, it is recommended that it should be taken 30 minutes or more prior to a meal. Therefore, we will request that patients take their daily ifetroban or placebo tablets first thing in the morning, at least 30 minutes before their breakfast.

Until institutional guidelines change, all subjects must obtain a negative COVID-19 test result within 72 hours prior to Visit 2. This is to ensure the safety of study staff during the pandemic due to aerosol-generating procedures that may occur at Visit 2. If the COVID-19 test comes back positive, the subject will be informed of their positive results and will be withdrawn from the study. They will receive a safety phone call one week later as follow-up.

Study staff will refer subjects to the current best PCR COVID test available advised by Infectious Disease.

Visit 2 After the 4-week treatment period, subjects will come into the ARC for **Visit 2**.

1. Interval history, physical exam, ACQ, SNOT-22, TNSS and spirometry will be recorded, along with FeNO.

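### The Visit 1 to Visit 2 changes in FEV1, ACQ, SNOT-22, FeNO and baseline LTE4 are tested without the Visit 1 value as a covariate, so an almost free gain in precision is left unused

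*Combined protocol and SAP*

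**What the plan says.** Section 3.3 defines the FEV1, ACQ and SNOT-22 outcomes as the change in the pre-aspirin value "at Visit 2 from Visit 1, compared between patients on placebo vs ifetroban". The synopsis defines the FeNO outcome in the same way: "Change from Visit 1 in baseline exhaled nitric oxide (FeNO) levels at Visit 2". Section 13.4.4 groups these four with baseline urinary LTE4 and compares each one "separately after 4 weeks of treatment with ifetroban or placebo using a two-sided two-sample t-test". It names no covariate.

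Everything needed for adjustment is collected at Visit 1, before the first dose of study drug. Section 8.3 lists "Interval history, physical exam, ACQ, SNOT-22, TNSS and spirometry will be recorded, along with FeNO", and for LTE4, "A urine sample will be collected for pregnancy and eicosanoid metabolites".

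The only covariate in the plan is provocative aspirin dose. It applies only to the aspirin-induced changes at Visit 2, of which section 3.3 says "we will also analyze these changes with provocative aspirin dose as a covariate". Section 13.4.3 (supportive analyses) is marked as not applicable and in any case concerns the primary endpoint.

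**The concern.** A pre-treatment measurement of the outcome can be used in two ways. Subtracting it fixes its coefficient at 1. Entering it as a covariate lets the data choose the coefficient, which under equal SDs is r. If r is well below 1, subtraction over-corrects and adds the noise of the Visit 1 measurement to the comparison.

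The trial aims for 20 completers per arm (section 13.7), and section 3.5 describes blocked allocation with no stratification factor. Two things follow. The planned test may have appreciably less power than the same data allow. And a chance difference between arms at Visit 1 carries into the estimated change in the one trial that is run. These outcomes bear on a stated aim: section 2.2 includes the effect of ifetroban on baseline lung function and symptom control.

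**Working it through.** **Inputs.** From section 13.4.4 (difference; SD; stated power): FEV1 6; 9.8; 78%. ACQ 0.35; 0.54; 82%. SNOT-22 9; 14; 86%. Baseline LTE4 0.14; 0.22; 80%. FeNO has neither SD nor power. Two-sided level 0.05. From section 13.7: 20 per arm. The SDs are introduced with "Based on our current internal clinical baseline data of 25 patients with AERD", so they are read as single-visit SDs. The correlation r is not in the documents. It is assumed over 0.3 to 0.9.

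**The plan's own figures.** A two-sample t-test with these SDs as they stand, 20 per arm and 38 df gives 47% (FEV1), 52% (ACQ), 51% (SNOT-22) and 50% (LTE4). It does not give 78, 82, 86 and 80%. If the SDs are single-visit and the test is on change, the stated powers are reached only at r = 0.76, 0.76, 0.79 and 0.76. The plan states no such value.

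**Formulas** (equal SDs at both visits):

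- Change score: variance 2·SD²·(1−r), 38 df.
- ANCOVA on Visit 1: variance SD²·(1−r²), multiplied by 1 + 1/36 = 37/36 for estimating the slope, 37 df.
- Ratio before the slope cost: (1−r²) / [2(1−r)] = (1+r)/2. The variance falls by 35% at r=0.3, 25% at 0.5, 15% at 0.7, 10% at 0.8 and 5% at 0.9.
- Break-even after the slope cost: (1+r)/2 × 37/36 = 1, so r = 2×36/37 − 1 = 0.946.

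**Example, SNOT-22 at r=0.5.** Change-score SD = 14·√(2×0.5) = 14.0, so the standard error is 14.0·√(2/20) = 4.43 and power is 51%. ANCOVA SD = 14·√(0.75×37/36) = 12.3, so the standard error is 3.89 and power is 62%.

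**Power at 20 per arm (noncentral t), change score → ANCOVA:**

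| r | FEV1 | ACQ | SNOT-22 | Baseline LTE4 |
|---|---|---|---|---|
| 0.3 | 36→50% | 39→54% | 39→53% | 38→53% |
| 0.5 | 47→57% | 52→62% | 51→62% | 50→61% |
| 0.7 | 68→74% | 73→79% | 73→78% | 72→77% |
| 0.8 | 85→87% | 88→91% | 88→90% | 87→90% |
| 0.9 | 99→99% | 99→99% | 99→99% | 99→99% |

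Simulation of 40,000 SNOT-22 trials agrees: 50.7% against 61.5% at r=0.5, and 88.1% against 90.3% at r=0.8. Both methods had a mean estimate of 9.0 points, so neither is biased on average.

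**As sample size.** The net variance ratio, (1+r)/2 × 37/36, is 0.668, 0.771, 0.874, 0.925 and 0.976 at r = 0.3, 0.5, 0.7, 0.8 and 0.9. Dividing 20 by it gives the number per arm that the change-score test would need for the same precision: about 29.9, 25.9, 22.9, 21.6 and 20.5.

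**Other reading of the SDs.** If the stated SDs were already SDs of change, the SNOT-22 t-test would have 51% power at any r. ANCOVA would have 68, 62, 56, 54 and 52% at the same five values of r. The direction is the same.

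**Chance imbalance.** One standard error of the Visit 1 SNOT-22 difference is 14·√(2/20) = 4.43 points. With the covariate slope equal to r, the change-score estimate moves by (1−r)×4.43: 2.2 points at r=0.5 and 0.9 points at r=0.8, against a target of 9.

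**The case against.** The strongest reply is that nothing here is wrong. A two-sample t-test on change is a recognised analysis, its standard error already allows for chance imbalance, and only non-primary outcomes are affected. All of that stands. The imbalance figures are the same efficiency argument seen in a single trial, not a second fault.

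The second reply is that the gain may be small. Section 4.2 requires stable asthma, and of background inhaled bronchodilators section 7.1.2 says "No modifications will be made in the course of the trial", so a high r is quite possible. If the stated powers are taken at face value as tests on change, they imply r of about 0.76 to 0.79. ANCOVA would then give 82, 86, 89 and 84% for FEV1, ACQ, SNOT-22 and LTE4, a gain of about 3 to 4 points. This is fair as to size, but it does not establish r. A one-sample or paired normal formula with 20 patients gives 78.2% (FEV1), 82.6% (ACQ) and 81.2% (LTE4), close to the stated figures. They may therefore come from a paired or crossover calculation; section 13.1 still calls the trial a crossover. That mismatch is a separate matter, and a covariate does not repair it.

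Two smaller points also stand. ACQ (mean 0.64, SD 0.54) and LTE4 (mean 0.37, SD 0.22) cannot be negative and are probably skewed, so the normal-theory powers are approximate. And baseline LTE4 is tested in 13.4.4, although the synopsis and section 3.3 list LTE4 or cysteinyl leukotrienes only for the aspirin-induced rise. Calling it a secondary outcome is therefore loose. None of these is a reason to leave out the covariate.

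**Conclusion.** The point holds. The plan uses the Visit 1 value less efficiently than it could. The direction is firm: with equal SDs, ANCOVA is the more precise analysis at 20 per arm unless r exceeds about 0.95.

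The size depends on r, which the plan does not give. The gain is about 14 to 15 power points at r=0.3, 10 to 11 at 0.5, 5 to 6 at 0.7, 2 to 3 at 0.8 and about 0.1 at 0.9. These figures assume equal SDs at the two visits, approximate normality, and the stated SDs read as single-visit SDs. The gain for FeNO cannot be quantified.

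The planned test remains valid and the primary PD2 analysis is untouched. The change is worth making because it costs almost nothing. Fixing it before the data are seen also avoids a later choice between adjusted and unadjusted results.

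**What to change.** In section 13.4.4, for FEV1, ACQ, SNOT-22, FeNO and baseline urinary LTE4, replace the two-sample t-test with a linear model of the pre-aspirin Visit 2 value on treatment and the Visit 1 value of the same measure. Modelling the change instead gives the same treatment estimate. Report the adjusted difference between arms with its 95% confidence interval. If a log scale is chosen for FeNO or LTE4, put both visits on it.

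The same sentence could cover the other Visit 1 to pre-aspirin Visit 2 changes in section 3.3 (other eicosanoids, tryptase, platelet measures), where the argument is identical.

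The cost is one sentence and one degree of freedom (37 instead of 38), with no new data, visits or patients.

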13.7 Sample Size Considerations

Assuming that there will be a dropout rate of 10-20%, we will seek to recruit 50 individuals with suspected AERD from our new referrals to meet a target sample size of 40 to complete the study, with 20 in each treatment arm. We will enroll additional subjects if we have an unusually high dropout rate. As detailed in section 13.4.2, with this sample size of 20 patients per treatment arm, we will have 83% power to detect a 3-fold shift in PD₂ (or an average an increase in PD₂ to 180 for patients on ifetroban, with a standard deviation of 170), at a 0.05 level of significance.

13. Identification and Access to Source Data**13.1. Source Data**

The Principal Investigator will keep accurate records to ensure that the conduct of the study is fully documented. Data derived from source documents will be transferred to protocol-specific CRFs. Hard copy results of the following clinical evaluations and clinical laboratory evaluations will be maintained in the participant's protocol-specific binder, housed at the Asthma Research Center:

- Patient medical histories, concomitant medications, adverse event forms (results written onto CRF)
- CBC/differential (printed copy)
- PFTs (printed copy)
- FeNO (results written onto CRF by coordinator/investigator)
- Pregnancy test (results written onto CRF by coordinator/investigator)
- Physical exam (results written onto CRF by coordinator/investigator)
- Patient questionnaires (results written onto CRF by patient)
- Details of which biologic specimens collected at each visit (written onto CRF by coordinator/investigator)

The applicable clinical study data will be transferred to a password-secured REDCap database on a dedicated server.

Data derived from research laboratory evaluations (flow cytometry, eicosanoid and cytokine levels, cellular assays) will be stored as a hard copy (as applicable) within laboratory notebooks, or within the appropriate assay-specific software program as required for each type of analysis.

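### The baseline urinary LTE₄ power statement equates 0.14 ng/mg Cr with a 30% fall when it is 38% of the stated mean, and its 80% power is not reproduced from the printed SD and 20 per arm

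*Combined protocol and SAP*

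**What the plan says.** Section 13.4.4 compares several baseline measures, urinary LTE₄ among them, "separately after 4 weeks of treatment with ifetroban or placebo using a two-sided two-sample t-test". For LTE₄ it estimates an average "of 0.37 ng/mg Cr and a standard deviation of 0.22". It then states "we will have 80% power to detect a difference of 0.14 ng/mg Cr (or a decrease in urinary LTE₄ of 30% from baseline" and describes that percentage as about half of what zileuton achieves, citing two outside studies. The significance level is 0.05.

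The LTE₄ sentence gives no sample size of its own. Section 13.7 sets a "target sample size of 40 to complete the study, with 20 in each treatment arm", after an assumed dropout of 10 to 20% from 50 recruited. The 25 patients mentioned in 13.4.4 are the source of the baseline estimates, not the trial's sample size.

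In the Synopsis and section 3.3, LTE₄ (or the cysLTs) is listed only for the rise during the aspirin reaction. The item covering Visit 1 to Visit 2 reads "Change in levels of other urinary, and nasal eicosanoids".

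**The concern.** One sentence gives two effect sizes as if they were the same, and they are not. The absolute difference is about a quarter larger than the percentage allows (0.14/0.111 = 1.26). Rounding cannot account for this. Item ii of the same section makes the same kind of conversion correctly, since 2.4 is 40% of 6.0, so dividing by the stated mean is the plan's own convention.

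At stake is how a null result would be understood. A reader who takes the sentence at face value would believe that the trial had 80% power against a 30% fall in baseline LTE₄. On the printed figures it has far less. The printed figures do not give 80% for the larger 38% fall either, so correcting the percentage alone would leave an unsupported power in the plan.

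**Working it through.** **Inputs.** Mean 0.37, SD 0.22, difference 0.14, percentage 30%, two-sided alpha 0.05 and a two-sample t-test (all 13.4.4); 20 per arm (13.7); allocation 1:1 (13.3).

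**1. Percentage against absolute effect.**
- 0.14 / 0.37 = 0.378, a 38% fall.
- 0.30 × 0.37 = 0.111 ng/mg Cr.

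**2. Attempt to reproduce the stated 80%.** With n per arm, the noncentrality is (difference/SD) × √(n/2) on 2n − 2 degrees of freedom. For n = 20 this is (difference/0.22) × √10 on 38 df, with critical value 2.024.
- Difference 0.14: standardised effect 0.636, noncentrality 2.012, power 50.1%.
- Difference 0.111: standardised effect 0.505, noncentrality 1.596, power 34.3%.

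The normal approximation gives 52% and 36%. A one-sided test at 0.05 gives 63% for 0.14. None of these is 80%.

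**3. What would give 80% at 0.14.**

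| Calculation | Power at 0.14 | Power at 0.111 |
|---|---|---|
| Plan as printed: SD 0.22, 20 per arm | 50% | 34% |
| SD 0.22, 25 per arm | 60% | 42% |
| SD 0.22, 40 per arm | 80% | 61% |
| Paired, normal approximation, n = 20, SD 0.22 | 81% | 62% |
| 20 per arm, SD back-solved to 0.154 | 80% | 60% |

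With SD 0.22, 80% power needs about 40 per arm for 0.14 and about 63 per arm for 0.111.

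**4. Sensitivity to the SD of change.** The comparison is of changes from baseline, so the SD of the change governs power. The documents do not give it. If the SD is 0.22 at each visit and the Visit 1 to Visit 2 correlation is ρ (an assumption), the SD of change is 0.22 × √(2(1 − ρ)). With 20 per arm:

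| ρ (assumed) | SD of change | Power at 0.14 | Power at 0.111 |
|---|---|---|---|
| 0.50 | 0.220 | 50% | 34% |
| 0.75 | 0.156 | 79% | 59% |
| 0.80 | 0.139 | 87% | 69% |
| 0.85 | 0.120 | 95% | 81% |

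No row gives 80% for both differences. An SD that makes 80% right for 0.14 leaves about 60% for a 30% fall. An SD that gives about 80% for a 30% fall gives about 95% for 0.14.

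**The case against.** The strongest reply is that 0.22 is the SD of a single baseline measurement, while the analysis uses change, whose SD may well be smaller. That is fair, and it limits what can be said about power. A reader might infer that the trial has at most 60% power for a 30% fall. The documents do not support that as a ceiling, because an assumed correlation of 0.80 or 0.85 gives 69% or 81%. The reply does not rescue the sentence, however. The percentage mismatch does not depend on any SD, and no single SD makes 80% true for both effects.

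A second reply is that this is one secondary comparison with no decision rule attached, and that readers would look at the confidence interval. That stands. The sample size rests on PD₂.

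Two stronger readings are tempting and should be resisted.
- A reader might take baseline LTE₄ to be the main human test of whether TP signalling drives cysLT overproduction. Section 3.3 gives the proof-of-mechanism role to the rise in cysLTs during the aspirin reaction, which has its own power statement.
- A reader might conclude that the outcome is not prespecified, because the endpoint lists omit it. Section 13.4.4 names it as a compared outcome, and the Schedule of Events collects urine eicosanoids at Visits 1 and 2. The omission is a cross-reference gap.

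The source of the 80% is also unknown. Using 40 per arm reproduces it, and so does a paired calculation, but nothing in the documents says that either was used. Nor do they show whether 0.14 or 30% was the intended effect.

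**Conclusion.** Wrong as written. The mismatch is arithmetic and needs no assumption: 0.14 ng/mg Cr is a 38% fall from 0.37, and a 30% fall is 0.111.

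The stated power is not reproduced. On the plan's own test, SD and completers per arm, it is about 50% for 0.14 and about 34% for 0.111. A figure of about 60% for a 30% fall is conditional: it holds if the 80% at 0.14 is accepted, which at 20 per arm implies an undocumented SD of about 0.154. Higher power for a 30% fall is possible only with a smaller SD of change that the documents do not give.

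The consequence is confined to how one secondary comparison is read. The primary analysis and sample size are unaffected.

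**What to change.** In section 13.4.4:
- Make the two effects agree, either as 0.14 ng/mg Cr (38%) or as 30% (0.11 ng/mg Cr).
- In the same sentence, restate the power with the n per arm and SD used. With 20 per arm and the printed SD this is about 50% for 0.14 or 34% for 0.11. If an SD of change is used instead, give its value and source and compute the power from it.
- Check the zileuton comparison against the corrected percentage. The cited studies are not part of these documents, so the sponsor has to do this.

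Replacing 30% by 38% and leaving the 80% in place would not be enough.

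Optionally, add the Visit 1 to Visit 2 change in urinary LTE₄ to section 3.3 and the Synopsis, so that the lists match 13.4.4.

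The cost is one revised sentence and, if wanted, one line in each list. Design, sample size and analysis method stay as they are. The stated power becomes less favourable unless a smaller SD of change can be documented.
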